 - b. Relationships between clinical and laboratory values will be evaluated in longitudinal mixed effect models. We will develop models that capture the combined frequency and severity of disease manifestations while accounting for age of onset, protoporphyria subtype (EPP and XLP), and genotype. A sample size of 150 (assuming a minimum of 3 follows ups per patient, a correlation of 0.7 among outcomes over time from the same subject, a variance of outcome equal to 1 and a compound symmetric covariance structure) yields 91% power to detect a moderate interaction ($\beta=0.4$) between time and an associated factor of interest.
 - c. A severity score based on predictive demographic and clinical characteristics will be developed
 - d. After 100 participants are enrolled, the mean score of the Hospital Anxiety and Depression Scale (HADS) will be computed and compared to the general population value. A sample size of 100 yields 90% power to detect a 20% difference in HAD-scale between the general population and our sample at the .05 significance level. The illness Perception Questionnaire and EPP/XLP-specific questionnaire will also be scored.
 - e. During this interim look at $n=100$, we will re-evaluate the estimates used in our initial power calculation that yielded a sample size of 150 and determine whether the study needs to be extended beyond this point to examine correlations of QoL scale scores with clinical severity and genotypes

Sponsors (federal, state, foundation and industry support): National institutes of Health (NIH)

1. Protocol Overview

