As with the Longitudinal Study of the Porphyrias, baseline visits can take place either (1) at a Participating Clinical Center (PCC), (2) arranged locally with the patient's own physician, with data and samples sent to the PCC, as needed, or (3) by telephone or email interview by the site coordinator, with data collected during the interview and arrangements made for sample collection, as needed. For visits where the participant cannot come to a PCC, all medical records must be forwarded to the site coordinator (including lab tests and physician notes). The questionnaires can be completed via phone, email or fax by the participant and sent to the site coordinator. For these visits the site coordinator is permitted to email the questionnaires to the participant and these can be returned by mail, email or fax. Once returned the coordinator should review them and if any issue need clarification contact the participant. The medical history and family history should be done via phone interview for the baseline visit.

If the study visits or sample collections takes place in facilities supported by the local institutions Clinical and Translational Science Award (CTSA), the protocol will be reviewed by any additional Advisory Committee, as appropriate, prior to implementation at the site. Centers in the Porphyrias Consortium may assist each other in data collection and data entry. The subject will be informed of the consortium arrangement and that their protected health information (PHI) will be shared with one or more other Porphyrias Consortium institutions, when approved by the IRB at each site. See Table 1 for the specific CRFs to be completed at Baseline.

Follow-up Assessments: New data as described below will be collected every 1-2 years, or more frequently if the subject experiences any significantly worsening porphyria-specific symptoms (liver disease, worsening sun sensitivity, etc) or has new study-related information to share with the study team. These overall scheduling plans may be modified based on clinical circumstances or if there is reason to anticipate a change in clinical course. Data collected during these follow-up visits will be entered onto the CRFs, see Table 1 for the specific CRFs to be completed for follow ups.

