Additional visits will be scheduled for participants who have experienced significant worsening of the disease as determined by the investigators (i.e. liver abnormalities, worsening sun sensitivity, etc). Such visits will be scheduled at the time of these events or shortly after, so that information will be current or recent and more likely to be accurate. Such visits may coincide with visits or hospitalizations for medical treatment. Data collected during these follow-up visits will be entered onto the General Medical History form under the Longitudinal Study of the Porphyrias and any appropriate Lab forms will be completed. Follow-up study visits are expected to take approximately 0.5-3 hours, depending on the testing required.

In order to accommodate participants' schedules, follow-up visits can take place within an acceptable window, defined as within one month of the schedule date. Visits that do not meet this expectation will still be permitted..

As with the Longitudinal Study of the Porphyrrias, follow-up visits can take place either (1) at a Participating Clinical Center (PCC), (2) arranged locally with the patient's own physician, with data and samples sent to the PCC, as needed, or (3) by telephone or email interview by the site coordinator, with data collected during the interview and arrangements made for sample collection, as needed. As with the baseline visit; when the participant cannot come to a PCC for follow up visits all medical records must be forwarded to the coordinator (including lab tests and physician notes). The questionnaires can be completed via phone, email or fax by the participant and sent to the site coordinator. The site coordinator is permitted to email the questionnaires to the participant and these can be returned by mail, email or fax. Once returned the coordinator should review them and if any issue need clarification contact the participant. The medical history and family history update should be done over the phone whenever possible, however if the participant is not able to be reached via phone this can be completed over email.

Data collected during follow-up visits is typically standard of care. Exceptions may include quality of life (Psychosocial) assessments, and collection of samples for the repository.

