 - Review of past medical records, including growth charts (for children), primary care and specialty evaluations and routine lab testing, and genetic testing (if previously done)
 - Physical examination

- Family history (complete pedigree)
- Laboratory tests (standard of care):
 - Hepatic Function Panel (including at minimum albumin, bilirubin total and direct, alkaline phosphatase, AST, ALT and total protein), CBC with differential, Serum Iron, TIBC, Ferritin, Vitamin D, and any other tests the investigators determines to be necessary for clinical management
 - Biochemical porphyria tests- erythrocyte protoporphyrin values (including free and zinc fractionation), and plasma total porphyrins [preferred lab is UTMB]
 - DNA test of the *FECH* or *ALAS2* genes as appropriate to be determined by the investigator
- Psychosocial questionnaires

Follow Up Visits:

- Clinical evaluation for changes in symptoms, signs, hospitalizations, other conditions, etc.
- Assessment of any ongoing EPP treatments
- Laboratory tests (standard of care):
 - Hepatic Function Panel (including at minimum albumin, bilirubin total and direct, alkaline phosphatase, AST, ALT and total protein), CBC with differential, Serum Iron, TIBC, Ferritin, Vitamin D, and any other tests the investigators determines to be necessary for clinical management
 - Biochemical porphyria tests- erythrocyte protoporphyrin values (including free and zinc fractionation), and plasma total porphyrins [preferred lab is UTMB]
- Psychosocial questionnaires

It is optimal to conduct follow-up visits at least once per year. Participants whose EPP symptoms are stable may be seen at 2 year intervals. More frequent study visits can be scheduled based on Interim Events (as described above) which may include changes in clinical course or treatment.

4.F. Sample Collection and Storage

4.F.1. Sample Collection

Samples (blood and urine) will be collected according to protocol for clinical laboratory testing (consistent with standard of care), porphyria-specific biochemical testing, molecular analysis, and specimen banking.

The following table outlines the specimens that will be requested for research alone. Samples collected for standard of care testing will be processed as normal per the institutions' procedures.

Specimens will be shipped monthly from Porphyrias Consortium sites to The Mount Sinai Porphyrias Repository (Icahn School of Medicine at Mount Sinai, New York, NY).

Table 2: Sample Collection Requirements

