6. Statistical Considerations

6.A Analysis Plan

General Statistical Considerations

Natural history study and genotype analyses: This is an observational study aimed to provide a systematic description of the severity and clinical course of each patient with the EPP phenotype, develop a severity score and correlate genotype with phenotype for EPP and XLP. Continuous variables representing patient demographic and clinical characteristics will be summarized using means and standard deviations or medians and quartiles as appropriate, while categorical variables will be summarized by frequencies with 95% confidence intervals.

A major objective will be to identify the FECH and ALAS2 mutations in each patient with the EPP-phenotype. In patients with the phenotype and no detectable FECH or ALAS2 mutations identified, a second independent blood sample will be obtained to confirm the absence of FECH and ALAS2 mutations, followed by whole exome sequencing. Exome analysis will be performed at the Mount Sinai Institute for Genomics and Multiscale Biology as described above in more detail.

Clinical and Laboratory Analyses: Clinical and laboratory measurements will be collected/described at each visit. We will develop models that capture the combined frequency and severity of disease manifestations while accounting for age of onset, protoporphyria subtype (EPP and XLP), protoporphyrin levels and genotype. To account for multiple observations obtained for each patient during the follow-up, we will develop linear mixed effects models that account for the main effect of interest and its change over time, correlated data associated with repeat measurements on the same persons, random effects of clinical center and patient, as well as the effects of confounding variables and any modifiers of the main effect. To assess the statistical significance of the effects of biochemical levels alone and these levels by age of patient, we will use a t-test to evaluate whether the coefficient of the interaction between biochemical level alone and biochemical levels by age differs from zero.

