- 1) Characterizing EPP and XLP Illness Perception via the Illness Perception Questionnaire, dermatology-specific QOL via the Dermatology Life Quality Index and EPP-specific QOL via the EPP/XLP specific questionnaire. The mean and standard deviation of each scale in our sample will be assessed.
- 2) Scores for all four QOL assessments will be analyzed; FECH and ALAS 2 mutations correlations will be sought with clinical parameters, disease severity score and genotypes.

Secondary analyses will inform whether a study extending beyond 100 patients will be needed to examine correlations of QOL scale scores with clinical severity and genotypes.

6. B Power Calculation

For the proposed analyses, the statistical powers are of two sided tests, with 0.05 level of significance.

Linear mixed effects model: We may assume, for example, that 150 participants will have at least 3 follow up visits per subject. Taking into account the correlation among outcomes over time from the same subject, the main interest is in determining whether the regression coefficient of the interaction between time and covariate of interest is zero or not. Using GPower 3.0, Table 6-1 shows the results when the variance of outcome is equal to 1, where ρ and β denote correlation among repeated outcome measures and effect size of the interaction, respectively. In this calculation, we assume compound symmetry for the covariance structure of repeated outcome measures from the same subject and the same number of subjects in each group with/without a potential factor of interest. The study is certain to detect moderate ($B \geq 0.4$) differences in the analysis.

Table 6-1. Power calculation for linear mixed effects model based on the most common types of porphyria (AIP and PCT)

Sample size	ρ	B for time x factor of interest	Power
150	0.5	0.3	0.45
		0.4	0.72
		0.6	>0.99
	0.7	0.3	0.67
		0.4	0.91
		0.6	>0.99

7. Data Management

All study data will be collected via systems created in collaboration with the RDCRN Data Management and Coordinating Center and will comply with all applicable guidelines regarding patient confidentiality and data integrity.

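### Clinical and laboratory values from worsening-triggered visits enter the section 6.A mixed models unmarked, which can bias the estimated course, usually toward apparent worsening after baseline

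*Combined protocol and SAP*

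**What the plan says.** **Visit rules.** Section 4.E.1 (Follow-up Assessments) plans data collection every 1-2 years, "or more frequently if the subject experiences any significantly worsening porphyria-specific symptoms". It adds: "Additional visits will be scheduled for participants who have experienced significant worsening of the disease". Investigators judge the worsening, and the visit is held at the event or soon after. Section 4.E.3 adds: "Participants whose EPP symptoms are stable may be seen at 2 year intervals".

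**Data at triggered visits.** Under Interim Events in 4.E.1, laboratory and medication forms are completed as needed. The Interim Event column of Table 1 marks medical history, medications, physical examination and three sets of laboratory tests as needed. It marks no questionnaire.

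**Analysis.** Section 6.A says clinical and laboratory measurements are collected at each visit, and continues: "To account for multiple observations obtained for each patient during the follow-up, we will develop linear mixed effects models". It gives no term for visit type, no restriction to scheduled visits and no model of visit timing. Section 4.I (second challenge) says status variables will often be handled as time-dependent covariates or change-point indicators, without linking them to the reason for a visit.

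**Visit frequency** is stated in three ways: every 1-2 years (4.E.1, 4.E.3), at least annually (Table 1 footnote) and once yearly (8.D). These passages must be reconciled, because the analysis needs to know which visits count as scheduled.

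**The concern.** The timing of an extra measurement depends on the patient's condition at that moment. If the modelled value is high, or is related to what is high, the extra visit samples a peak. Baseline has no such visits and follow-up does, so the follow-up mean rises even when nothing has changed. A random patient intercept absorbs stable differences between patients. It does not absorb a transient rise that itself caused the visit.

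At stake are the clinical and laboratory descriptions of natural history, and in particular the question in 4.H.2 of whether porphyrin levels are stable over time. A spurious rise would bear directly on that answer. The bias discussion in 4.G and 4.I covers survival, severity and access to care, but not visit timing.

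**Working it through.** **1. The plan's own figure and scale.** Inputs from 6.B: "150 participants will have at least 3 follow up visits per subject"; results "when the variance of outcome is equal to 1"; "the statistical powers are of two sided tests, with 0.05 level of significance"; equal groups; compound symmetry. From the Synopsis: "a correlation of 0.7 among outcomes over time from the same subject". Take baseline plus 3 follow-ups at times 0 to 3 (sum of squared deviations 5), and read B = 0.4 as the total divergence over follow-up.

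- SE per interval = sqrt[(1 - 0.7)/5 × 4/150] = sqrt(0.0016) = 0.040
- Effect per interval = 0.4/3 = 0.133; ratio 3.33
- Power = Φ(3.33 - 1.96) = 0.915, against the stated 0.91

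At correlation 0.5 the same formula gives 0.733 against 0.72. No single reading reproduces all of Table 6-1, but the scale is clear: outcome SD 1, so the shifts below are in SD units.

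**2. Assumptions the documents do not supply.** These are the trigger rate, the threshold, the persistence of a flare, and how closely the trigger follows the outcome.

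**3. Hand check.** Suppose a visit is triggered when the within-patient fluctuation exceeds 1.5 of its own SDs. The mean of a standard normal above 1.5 is 0.1295/0.0668 = 1.94. In outcome SDs the excess is 1.94 × sqrt(1 - ρ): 1.06 at ρ = 0.7 and 1.37 at ρ = 0.5. Take 0.8 triggered visits per patient beside 3 to 5 scheduled follow-ups:

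- Triggered share = 0.8/5.8 to 0.8/3.8 = 0.14 to 0.21
- Approximate false shift = 0.15 to 0.22 SD (ρ = 0.7), or 0.19 to 0.29 SD (ρ = 0.5)

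**4. Simulation, no true change.** 150 patients, 5 years in monthly steps, within-patient autocorrelation 0.8 per month, the 1.5 threshold, and 2-year spacing after a stable visit. A random-intercept (compound-symmetry) model is fitted to all visits with a baseline/post-baseline term. Ranges cover ρ = 0.5 and 0.7.

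| Triggered visits per patient | False post-baseline shift (SD) | False positives |
|---|---|---|
| 0.1 | 0.05 | 11-14% |
| 0.3 | 0.07 to 0.10 | 30-33% |
| 0.8 | 0.17 to 0.22 | about 95% |
| 1.8 | 0.25 to 0.32 | 99-100% |

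At 0.8 visits, scheduled visits alone give about 0.015 SD (4-7% false positives). All visits with a triggered-visit indicator give 0.009 to 0.013 SD (3-4%).

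Two further simulations agree:
- At 0.4 to 1.1 triggered visits the shift is 0.08 to 0.25 SD (34-99% false positives). Either remedy brings it to at most 0.02 SD (2-7%).
- On a quarterly grid (autocorrelation 0.6, correlation 0.5, triggered visits 14-29% of the data) the shift is 0.13 to 0.24 SD (52-96%).

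**5. What changes the answer.**
- *Trigger only related to the outcome.* The excess in step 3 scales with the trigger-outcome correlation r, so r = 0.5 turns 0.08-0.25 SD into about 0.04-0.125 SD. On the quarterly grid the fall was smaller: 0.10-0.15 SD at r = 0.5 and 0.06-0.11 SD at r = 0.25.
- *Linear time instead of a step.* Bias is 0.005 to 0.017 SD per year at 0.4 to 1.1 triggered visits (10-24% false positives). Across the wider range in the table it is 0.008 to 0.033.
- *Time by factor (ρ = 0.7).* With equal triggering the bias is about zero (-0.004 SD). With monthly flare capture of 0.30 in one group and 0.05 in the other it is +0.11 SD on the step term, or 0.064 SD over 5 years on a linear slope.
- *Enrolment during a flare (ρ = 0.7).* With 10%, 20% and 30% of patients enrolled in a flare, the pooled shift is +0.07, -0.04 and -0.13 SD.
- *The 2-year interval alone.* 0.002 to 0.009 SD.

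**The case against.** The strongest reply is that 6.A never says triggered values are pooled; that is inferred from silence, and 4.I mentions change-point indicators. This stands in part, since a reader should not take the plan to state pooling outright. But 4.E.1 lists interim visits among the study visits and treats worsening visits as follow-up visits, and 6.A models the observations obtained during follow-up. Followed as written, triggered values enter. The indicators in 4.I describe patient status, are used often rather than by rule, and are not tied to visit type.

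A second reply is that the trigger is symptoms or liver abnormality as judged by the investigator, and no section says porphyrin levels rise with these. That stands, and it is why the lower range for a moderate correlation is given.

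A third is that the large figures belong to a before/after-baseline step, whereas the plan is sized on a time interaction. That also stands: slope bias is small.

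Four stronger readings are tempting, but the documents do not support them:
- *The 2-year interval causes the bias.* It depends on values already observed and contributes almost nothing.
- *The sized time-by-factor effect is biased in general.* It is not when factor levels trigger equally. Nor can 0.11 SD be set firmly against B = 0.4, because 6.B gives B no time scale.
- *The HADS result is at risk.* It is a one-sample comparison, and Table 1 has no HADS at interim events.
- *Visit type is already captured.* The columns of Table 1 show which forms are due, not a stored field. Worsening visits use forms also used at routine follow-up, and 4.E.1 permits out-of-window visits.

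**Conclusion.** The concern holds for the clinical and laboratory mixed models. The protocol creates measurements whose timing depends on the patient's condition, and 6.A does not distinguish them. Under the assumed 0.4 to 1.1 triggered visits per patient over 5 years, a model comparing follow-up with baseline could show a false shift of about 0.08 to 0.25 SD if the outcome is the trigger, and about half that if the two are moderately correlated. Slope bias is about 0.005 to 0.02 SD per year, with roughly 10-24% false positives. The usual direction is apparent worsening, but it is not fixed: enrolment of 20-30% of patients during a flare reversed it. So the plan can produce a false course; it cannot be said that it will. The size rests on trigger frequency, flare persistence and trigger-outcome correlation, none of which the documents give.

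**What to change.** In 6.A, state that:

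1. the main longitudinal models of clinical and laboratory outcomes use baseline and scheduled follow-up visits with actual visit times, or all visits with a triggered-visit indicator, and name which of the two is chosen;
2. Interim Events and worsening-triggered visits are analysed as event counts;
3. the alternative in item 1 is reported as a sensitivity analysis.

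Record a flag in the database for each visit, scheduled or triggered, and reconcile the statements on visit frequency so that the flag has a clear definition.

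No visit or care changes. The cost is that some measurements leave the main model under the first option, and one data field may be needed. Neither option corrects for patients who enrol during a flare. With 20% so enrolled and no triggered visits at all, the simulated shift was still -0.198 SD, so that limitation should be stated when results are reported.
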